### **7.1.5.2. Incomplete Dates**

All AEs with partial onset dates will be identified and the partial dates will be imputed for TEAE determination. The imputation rules are as follows:

- If day and month are missing but year is available, then the imputed day and month will be 01Jan or the first dosing date if they have the same year, whichever is later.
- If day is missing but the month and year are available, then the imputed day will be the first day of the month or the first dosing date if they have the same month and year, whichever is later.
- AEs with completely missing onset dates and stop dates, or with the onset date missing and a stop date later than the first dosing date of andecaliximab/placebo, will be considered to be treatment emergent. In addition, an AE with the onset date missing and an incomplete stop date with the same or later month and year (or year alone if month is not recorded) as the first dosing date of study drug will be considered treatment emergent.

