#### **6.2.12. Adverse Events**

From the time of obtaining informed consent through the first administration of study drug, record all SAEs as well as any AEs related to protocol-mandated procedures on the AE eCRF. All other untoward medical occurrences observed during the screening period, including exacerbation or changes in medical history are to be captured on the medical history eCRF.

From the time of the first administration of study drug through 55 days post the last administration of treatment (GS-5745/placebo and mFOLFOX6), record any SAEs, and AEs including exacerbation or changes in medical history, on the AE eCRF.

See Section 7 Adverse Events and Toxicity Management for additional details.

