## **7.1.5. Treatment-Emergent Adverse Events**

### **7.1.5.1. Definition of Treatment-Emergent**

Treatment-emergent AEs (TEAEs) are events in a given study period that meet any of the following criteria:

- Any AEs with onset date of on or after andecaliximab/placebo start date and no later than 30 days after permanent discontinuation of all study treatment (andecaliximab /placebo and chemotherapy) or
- Any AEs with onset date of on or after the andecaliximab/placebo start date and no later than 55 days after permanent discontinuation of andecaliximab/placebo or
- AEs leading to discontinuation of andecaliximab/placebo

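### The rule for partial AE onset dates ignores a known stop date, so an event that ended before the first dose can be classified as treatment-emergent

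*SAP*

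**What the plan says.** SAP 7.1.5.2 (Incomplete Dates) sets its scope first: "All AEs with partial onset dates will be identified and the partial dates will be imputed for TEAE determination". Three bullets follow.

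- Day and month missing, year known: "the imputed day and month will be 01Jan or the first dosing date if they have the same year, whichever is later".
- Day missing, month and year known: "the imputed day will be the first day of the month or the first dosing date if they have the same month and year", again taking the later of the two.
- Onset wholly missing: the event counts if the stop date is missing too. An event "with the onset date missing and a stop date later than the first dosing date of andecaliximab/placebo, will be considered to be treatment emergent". An incomplete stop date also qualifies when its known part is the same as, or later than, that of the first dosing date.

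The stop date appears only in the third bullet.

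SAP 7.1.5.1 then uses the resulting onset. The first criterion is "Any AEs with onset date of on or after andecaliximab/placebo start date and no later than 30 days after permanent discontinuation of all study treatment", so an onset imputed to the first dosing date meets its lower limit.

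On collection before dosing, Protocol 6.2.12 tells sites to "record all SAEs as well as any AEs related to protocol-mandated procedures on the AE eCRF" between consent and first administration. For the rest: "All other untoward medical occurrences observed during the screening period, including exacerbation or changes in medical history are to be captured on the medical history" form.

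**The concern.** Imputing towards treatment-emergent is a sound default when nobody knows whether an event began before or after the first dose. A stop date before the first dose settles the matter: the event cannot have begun on treatment. The two partial-date bullets discard that information and place the onset on a day when the event was already over.

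The section is also uneven. The third bullet does not bring in the same event if its onset is wholly missing. Recording the month of onset, which is more information, moves the event into the treatment-emergent group.

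This runs against the rest of the plan. Protocol 8.6 and SAP 7 send pre-treatment data to listings, and Protocol 8.6.2 defines a treatment-emergent event by onset on or after the first dose. SAP 7.4.2 makes the corresponding check for concomitant medications: those stopped on or before the first dosing date are excluded, with a rule for partial stop dates. The AE rule has no such check.

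At stake is the accuracy of the counts in SAP 7.1.6.1. Every SAE from consent onwards is on the AE form, so an affected record could enter the TEAE, Grade 3 or higher and treatment-emergent SAE tables.

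**Working it through.** The documents give no figure on this point. The check has two parts: apply the rule literally to an example, then ask how often its trigger would be met.

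**1. The rule applied.** Inputs: the bullets of SAP 7.1.5.2 and the first criterion of SAP 7.1.5.1. The example dates are illustrative: first dose 10 Mar 2017, stop date 05 Mar 2017.

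| Recorded onset | Rule | Imputed onset | Treatment-emergent? |
|---|---|---|---|
| Unknown day, Mar 2017 | later of 01 Mar and 10 Mar | 10 Mar 2017 | Yes |
| Unknown day and month, 2017 | later of 01 Jan and 10 Mar | 10 Mar 2017 | Yes |
| Unknown day, Feb 2017 | month differs, so first of month | 01 Feb 2017 | No |
| Wholly missing | stop date must be after 10 Mar; it is 05 Mar | none | Not brought in |

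In the first two rows the imputed onset is 10 − 5 = 5 days after the recorded stop. With a stop-date check both rows become not treatment-emergent, and the other two rows do not change.

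**2. How often the trigger is met.** For an onset partial by day only, the misclassification needs the onset to fall in the calendar month of the first dose. Inputs: a screening period of up to 28 days (Protocol 3.3). Assumptions, because the documents give nothing on these: onset is equally likely on each eligible day of a 28-day screening period, first-dose dates are spread evenly over the calendar, and the event lasts *L* days.

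To have stopped at least one day before the first dose, the event must start between *L* + 1 and 28 days before it. The mean lead time is (*L* + 1 + 28)/2 days. With an average month of 30.4375 days, the chance of sharing the month is about 1 − (mean lead)/30.4375.

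- *L* = 3: mean lead 16.0; 1 − 16.0/30.4375 = 0.47
- *L* = 7: mean lead 18.0; 1 − 18.0/30.4375 = 0.41
- *L* = 10: mean lead 19.5; 1 − 19.5/30.4375 = 0.36
- *L* = 14: mean lead 21.5; 1 − 21.5/30.4375 = 0.29

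Counting actual calendar days, over 1464 consecutive first-dose dates from 1 Jan 2016, gives the same values: 47%, 41%, 36% and 29%. If resolution before dosing is not required (onset anywhere from 1 to 28 days before), the count gives 52%. That is the wrong population here, because only events that ended before dosing are misclassified.

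For an onset known only to the year, the same argument with 365.25 days gives 1 − 16.0/365.25 = 0.96 for *L* = 3 and 1 − 21.5/365.25 = 0.94 for *L* = 14.

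All these figures are conditional on a partial onset date. The documents do not say how common those are, so the figures do not give a number of affected events.

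**The case against.** The strongest reply is that the combination will hardly ever arise. It needs a pre-dose SAE or procedure-related AE, a partial onset that matches the first dosing date, and a stop date known to be earlier. Other screening events go to medical history and never meet the rule. Protocol 9.1.5 requires AE start and end dates in the source, and 9.1.6 has discrepancies queried. Protocol 7.3.2.1 has SAEs transmitted within 24 hours of the investigator's knowledge, and SAP 7.1.4 has them reconciled with the safety database. An event within a short screening period whose onset day and month are both unknown is hard to picture, so the high year-only figure carries little weight. All of this stands: it limits the size of the problem but does not change what the rule does.

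A second reply is that over-counting harm is conservative. That holds when timing is uncertain, not when a known stop date has removed the uncertainty.

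A third is that the contrast with the third bullet rests partly on silence, since that bullet lists only what is treatment-emergent. That is fair. But an event with no onset and an early stop date satisfies none of its conditions, and nothing else brings the event in by date.

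A reader might go further and infer that such records are already in the data, or that outputs will show onsets later than stop dates. The documents support neither. They show only that such records can occur. They limit the imputation to deciding treatment-emergent status, so the dates displayed in listings need not change.

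**Conclusion.** The rule is wrong as written. SAP 7.1.5.2 classifies as treatment-emergent an event whose stop date shows that it ended before the first dose, and nothing elsewhere in the SAP or protocol corrects this. The conclusion rests on the text alone.

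The effect is small. Few events, possibly none, would be affected. The 30% to 50% range applies only to resolved pre-dose events with the onset day missing, and it rests on the assumed 3- to 14-day durations and uniform onset. It should not be read as saying that half of all screening events are misclassified.

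Nor should the point be read as a bias in the safety comparison. The rule is identical in both arms of a double-blind trial and concerns events before dosing, so the expected effect is a slight over-count rather than an advantage to one arm. No efficacy analysis, alpha level or power figure depends on it. This is a low-priority correction.

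**What to change.** Add the following to both partial-date bullets of SAP 7.1.5.2:

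> If the AE stop date is before the first dosing date of andecaliximab/placebo (complete date earlier; or, if partial, its recorded month and year, or year alone if month is not recorded, earlier than that of the first dosing date), the AE is not treatment-emergent. Otherwise the imputation above applies.

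This covers partial stop dates in the way the third bullet already does. It keeps the cautious default wherever the stop date is missing, later, on the day of the first dose, or too incomplete to settle the order. The cost is one sentence per bullet and one programming condition. No genuine treatment-emergent event is lost, because an event that ended before the first dose cannot have started on or after it.

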## **7.1.6. Summaries of Adverse Events and Deaths**

Treatment-emergent AEs will be summarized based on the Safety Analysis Set.

### **7.1.6.1. Summaries of AE Incidence by Severity**

The number and percentage of subjects who experienced at least 1 TEAE will be provided and summarized by SOC, PT, maximum severity, and treatment group. For other AEs described below, summaries will be provided by SOC, PT, and treatment group:

- any TEAE
- any Grade 3 or higher TEAE

- any TE SAE
- any TEAE leading to andecaliximab/placebo dose interruption
- any TEAE leading to 5-FU bolus dose modification or interruption
- any TEAE leading to 5-FU infusion dose modification or interruption
- any TEAE leading to oxaliplatin dose modification or interruption
- any TEAE leading to andecaliximab/placebo discontinuation
- any TEAE leading to 5-FU bolus discontinuation
- any TEAE leading to 5-FU infusion discontinuation
- any TEAE leading to oxaliplatin discontinuation
- any TEAE leading to death
  - AE leading to death disease related
  - AE leading to death not disease related

For TEAEs, Grade 3 or higher TEAEs, and SAEs, the summary of AEs will be further categorized into related to andecaliximab/placebo, related to 5-FU bolus, related to 5-FU infusion, and related to oxaliplatin.

A brief, high-level summary of AEs described above will be provided by treatment group and by the number and percentage of subjects who experienced the above AEs.

Multiple events will be counted only once per subject in each summary. Adverse events will be summarized and listed first in alphabetic order of SOC (if applicable), and then by PT in descending order of total frequency within each SOC. For summaries by severity grade, the most severe grade will be used for those AEs that occurred more than once in an individual subject during the study.

In addition to the above summary tables, TEAEs, Grade 3 or higher TEAEs, SAEs, TEAEs leading to death, andecaliximab /placebo-related AEs, and TEAEs leading to discontinuation of andecaliximab /placebo will be summarized by PT only in descending order of total frequency.

Death will be summarized by whether it is considered as treatment emergent and the cause of the death (AE, due to PD, or other reasons).

Data listings will be provided as follows:

- AEs
- AEs with Grade 3 or higher
- SAEs
- AEs leading to andecaliximab/placebo interruption
- AEs leading to 5-FU bolus modification or interruption
- AEs leading to 5-FU infusion modification or interruption
- AEs leading to oxaliplatin modification or interruption
- AEs leading to andecaliximab/placebo discontinuation
- AEs leading to 5-FU bolus discontinuation
- AEs leading to 5-FU infusion discontinuation
- AEs leading to oxaliplatin discontinuation
- AE leading to Death
- All Deaths

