**Treatment:**

Treatment will occur over cycles comprised of 28 days. Subjects who meet eligibility will undergo CT or MRI scan performed every 8 weeks. Beginning with Day 1 of Cycle 1, subjects will receive GS-5745 or placebo by intravenous infusion over 30 minutes every 2 weeks for a total of 2 infusions per cycle (Day 1 and Day 15 of each cycle). All subjects will also receive mFOLFOX6 for the first 6 cycles and 5-fluorouracil (5-FU) and leucovorin (LV) thereafter administered via intravenous infusion after GS-5745 or placebo on Days 1 and 15 of each cycle. The mFOLFOX6 dosing regimen will consist of *l*-LV 200 mg/m^2 or *dl*-LV 400 mg/m^2 and oxaliplatin 85 mg/m^2 followed by bolus 5-FU 400 mg/m^2 and a 46-hour infusion of 5-FU 2400 mg/m^2.

Treatment will continue with subsequent 28-day treatment cycles in combination with intravenous mFOLFOX6 for a total of 12 infusions over 6 cycles via the same regimen defined above. After the subject has received 6 cycles of mFOLFOX6, the oxaliplatin component will be discontinued, and 5-FU, leucovorin, and GS-5745/placebo will be continued as maintenance therapy in the absence of disease progression or toxicity warranting discontinuation of therapy. CT or MRI for assessment of tumor status will be conducted every 8 weeks. However, tumor response may be assessed prior to the specified every 8-week time point, if clinically indicated.

---

**Investigational Drug:** Subjects will be administered 800 mg GS-5745/placebo intravenous over approximately 30 minutes and in advance of mFOLFOX6 on Days 1 and 15 of each cycle.

---

**Reference Therapy, Dose, and Mode of Administration:** The dosing regimen for each subject will adhere to the protocol specifications. mFOLFOX6 will consist of *l*-LV 200 mg/m^2 or *dl*-LV 400 mg/m^2 and oxaliplatin 85 mg/m^2 followed by bolus 5-FU 400 mg/m^2 and a 46-hour infusion of 5-FU 2400 mg/m^2.

---

**Criteria for Evaluation:** All subjects meeting the eligibility criteria that have signed a consent form and have begun treatment will be evaluated for response.

Efficacy

Overall survival (OS) is the primary endpoint of the study and is measured as time from date of randomization to death from any cause.

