### **8.6.2. Adverse Events**

Clinical and laboratory adverse events will be coded using the Medical Dictionary for Regulatory Activities (MedDRA). System Organ Class (SOC), High-Level Group Term (HLGT), High-Level Term (HLT), Preferred Term (PT), and Lower-Level Term (LLT) will be attached to the clinical database.

Events will be summarized on the basis of the date of onset for the event. A treatment-emergent adverse event is defined as any adverse event with onset date on or after the date of first dose of study drug up to 55 days after permanent study drug discontinuation or any adverse events leading to premature study drug discontinuation.

Summaries (number and percentage of subjects) of treatment-emergent adverse events (by SOC, HLT, and PT) will be provided by treatment group.

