### 8.11. Sample Size

Assuming a median OS time for the mFOLFOX6 + placebo group of 11.5 months, 286 events are needed to detect a hazard ratio (HR) of 0.70 with 85% power at a 1-sided significance level of 0.025 using a log-rank test, given 1 efficacy interim at 66.7% information. With an accrual period of 18 months, minimum follow-up of 18 months, and a 10% annual dropout rate, a total sample size of 430 subjects (215 subjects per treatment group) is needed to observe the required 286 events within the given time frame.

As the targeted number of deaths is large (~286), if the null hypothesis of the primary end point of OS is rejected, it will convincingly demonstrate clinical treatment effect and would provide a narrow confidence interval. Based on the number of deaths and the assumed treatment effect on OS in the protocol, the expected 95% confidence interval on HR of OS between the 2 treatment groups is approximately (0.627, 0.996). At the time of final analysis and assuming OS is significant, PFS will be tested at one-sided type I error of 0.016. Assuming that the hazard ratio for PFS is 0.7, which is expected to be on par or better than the treatment effect in OS, and that median PFS for the control is 9 months, a sample size of 430 subjects (322 PFS events) will provide 85% power under the planned study enrollment (18 months), follow-up duration (18 month), and drop-out rate (annually 10%).

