### 1.1. Study Objectives

The primary objective of this study is as follows:

- To compare the efficacy of andecaliximab (GS-5745) versus placebo in combination with mFOLFOX6 as measured by overall survival (OS)

The secondary objectives of this study are as follows:

- To compare the efficacy of andecaliximab versus placebo in combination with mFOLFOX6 as measured by progression-free survival (PFS)
- To compare the efficacy of andecaliximab versus placebo in combination with mFOLFOX6 as measured by objective response rate (ORR) per Response Evaluation Criteria In Solid Tumors version 1.1 (RECIST v1.1)
- To compare the safety of andecaliximab versus placebo in combination with mFOLFOX6

The exploratory objectives of this study are as follows:

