### 1.2. Study Design

This is a Phase 3, randomized, double-blind, multicenter study of andecaliximab combined with mFOLFOX6 in subjects with untreated gastric and GEJ adenocarcinoma. A total of 430 eligible subjects with advanced gastric and GEJ cancer will be randomized in a 1:1 manner to receive mFOLFOX6 plus andecaliximab or mFOLFOX6 plus placebo. Treatment assignment will be stratified by ECOG status (0 or 1), geographic region (Latin America or other participating countries), and primary tumor site (gastric or GEJ).

[figure not shown]

Computed tomography (CT) or magnetic resonance imaging (MRI) scans will be performed every 8 weeks to evaluate response to treatment by RECIST v1.1.

Dosage and frequency will be as follows:

- mFOLFOX6 on Days 1 and 15 of each 28-day treatment cycle for a total of 6 cycles followed thereafter by leucovorin (LV) and 5-fluorouracil (5-FU) dosing on Days 1 and 15 of each 28-day treatment cycle until disease progression. The mFOLFOX6 dosing regimen will consist of *l*-LV 200 mg/m^2 or *dl*-LV 400 mg/m^2 and oxaliplatin 85 mg/m^2 followed by bolus 5-FU 400 mg/m^2 and a 46-hour infusion of 5-FU 2400 mg/m^2.
- Andecaliximab /Placebo 800 mg every 2 weeks until disease progression

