### 1.3. Sample Size and Power

Assuming a median OS time for the mFOLFOX6 + placebo group of 11.5 months, 286 OS events are needed to detect a hazard ratio (HR) of 0.70 with 85% power at a 2-sided significance level of 0.05, given 1 efficacy interim at 66.7% information. With an accrual period of 18 months, minimum follow-up of 18 months, and a 10% annual dropout rate, a total sample size of 430 subjects (215 subjects per treatment group) is needed to observe the required 286 OS events within the 36-month time frame.

As the targeted number of OS events is large (~286), if the null hypothesis of the primary end point of OS is rejected, it will convincingly demonstrate clinical treatment effect and would provide a narrow confidence interval. Based on the number of deaths and the assumed treatment effect on OS in the protocol, the expected 95% confidence interval on the HR of OS between the 2 treatment groups is ~ (0.627, 0.996). At the time of final analysis and assuming OS is significant, PFS will be tested at one-sided type I error of 0.016. Assuming that the hazard ratio in PFS is 0.7, which is expected to be on par or better than the treatment effect in OS, and that median PFS in control is 9 months, a sample size of 430 subjects (322 PFS events) will provide 85% power under the planned study enrolment (18 months), follow-up duration (18 month), and drop-out rate (annually 10%).

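### Treatment and the adverse-event window run to progression, but AEs are compared only as crude percentages; if PFS differs as assumed, exposure alone could shift them by about 2 to 7 points

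*SAP*

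**What the plan says.** **Objective.** SAP 1.1 lists as a secondary objective "To compare the safety of andecaliximab versus placebo in combination with mFOLFOX6". Protocol 2.2 and 8.1.2 carry the same objective.

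**Treatment duration.** SAP 1.2 gives "Andecaliximab /Placebo 800 mg every 2 weeks until disease progression", and for leucovorin and 5-FU after the sixth cycle "dosing on Days 1 and 15 of each 28-day treatment cycle until disease progression". Oxaliplatin is capped in both arms. The protocol synopsis states "After the subject has received 6 cycles of mFOLFOX6, the oxaliplatin component will be discontinued".

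**Counting window.** Under SAP 7.1.5.1 an AE is treatment-emergent from the first dose of study drug until 55 days after study drug stops, or until 30 days after all study treatment stops. Protocol 8.6.2 also uses 55 days after study drug. The window therefore follows treatment duration.

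**AE measure.** Protocol 8.6.2: "Summaries (number and percentage of subjects) of treatment-emergent adverse events (by SOC, HLT, and PT) will be provided by treatment group". SAP 7.1.6.1: "The number and percentage of subjects who experienced at least 1 TEAE will be provided". Each subject counts once per summary. Treatment-emergent laboratory abnormalities (SAP 7.2.2.2) are also counts and percentages.

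**Exposure.** SAP 4.2.1 tabulates duration, number of doses and adherence by arm. None of these is used as a denominator for AEs.

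**Expected PFS difference.** Protocol 8.11: "Assuming that the hazard ratio for PFS is 0.7", with a control median of 9 months. SAP 1.3 repeats the assumption.

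**The concern.** When patients stay on treatment until progression, the arm with longer PFS is watched longer for AEs. A percentage of subjects with at least one event rises with time at risk even when the underlying hazard is the same. The plan's efficacy assumption therefore implies unequal observation for its safety comparison.

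The direction depends on the PFS result. With a PFS benefit, events that keep arising during maintenance (fatigue and infection are plausible examples) would look more frequent on andecaliximab without any added hazard. With shorter treatment on andecaliximab, the same tables would hide added toxicity. The first case is the one in which the benefit-risk reading matters most. A reader of the planned tables could see the exposure imbalance but could not correct for it.

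**Working it through.** **1. The plan's own PFS figure.** SAP 1.3 states 322 PFS events and 85% power at one-sided 0.016. By Schoenfeld's formula, power = Φ(½√322 × |ln 0.70| − z₀.₉₈₄) = Φ(8.972 × 0.3567 − 2.144) = Φ(1.056) = 0.854. With exponential PFS, 18 months' uniform accrual, 18 months' minimum follow-up and 10% annual dropout, the expected number of PFS events is 321. The stated figures reproduce.

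**2. Time on treatment.** Assume exponential PFS with treatment stopping only at progression. The monthly hazards are r = ln 2/9 = 0.0770 on placebo and 0.70 × 0.0770 = 0.0539 on andecaliximab, so the medians are 9.0 and 9/0.70 = 12.9 months. The planned accrual and follow-up put the data cut c between 18 and 36 months after randomisation. Mean time on treatment is the average over c of (1 − e^(−rc))/r:

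| Assumption | Placebo | Andecaliximab | Ratio |
|---|---|---|---|
| Data cut at 18 to 36 months | 11.2 | 14.1 | 1.25 |
| Plus 10% annual dropout | 10.4 | 12.9 | 1.24 |
| Plus 5% per month other stopping (assumed) | 7.6 | 9.0 | 1.18 |
| No data cut | 13.0 | 18.5 | 1.43 |

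The third row replaces the 10% dropout with the assumed 5% per month.

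**3. Crude incidence with no drug effect.** Give both arms the same constant AE hazard h per month, and let w = 55 days = 1.807 months. For a cut at c,

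P(AE) = 1 − e^(−hw) × [ r/(r+h) × (1 − e^(−(r+h)c)) + e^(−(r+h)c) ],

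averaged over c from 18 to 36.

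Worked case, 40% on placebo: this requires h ≈ 0.0446.
- Placebo: r+h = 0.1216 and the average of e^(−(r+h)c) is 0.045. P = 1 − 0.923 × (0.633 × 0.955 + 0.045) = 0.40.
- Andecaliximab: r+h = 0.0985 and the average is 0.080. P = 1 − 0.923 × (0.547 × 0.920 + 0.080) = 0.46.

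| Placebo | Andecaliximab, cut + 55 days | With 5%/month other stopping | No cut, no window |
|---|---|---|---|
| 20% | 23.8% (+3.8) | 22.5% (+2.5) | 26.3% (+6.3) |
| 40% | 46.1% (+6.1) | 43.8% (+3.8) | 48.8% (+8.8) |
| 60% | 66.6% (+6.6) | 63.9% (+3.9) | 68.2% (+8.2) |

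Truncating the 55-day window at the cut as well gives +3.6, +5.9 and +6.5. The last column uses λ/(λ + 0.70) with λ = p/(1 − p), for example 0.25/0.95 = 0.263. It is a ceiling because it ignores the planned cut. At a PFS hazard ratio of 0.80, the data-cut excesses are 2.4, 3.9 and 4.2 points.

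In subjects, 6.1 points of 215 is about 13. A nominal two-sided 5% comparison would flag such a row with probability 0.15 at 20% incidence and 0.28 at 50%.

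**4. Events that do not accumulate.** Six cycles of 28 days are 5.52 months. Mean time within that limit is 4.50 versus 4.77 months, a ratio of 1.06. For events confined to it, the excess at 20 to 60% incidence is 0.9 to 2.3 points with a 30-day tail and 1.2 to 2.9 with none. It is about 0.4 to 1.2 if the risk continues through the 55-day window. For events confined to the first two months it is 0.4 to 1.1 points.

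**5. Would one rate per subject-year repair this?** With a constant hazard the rate ratio is 1.00, as it should be. With equal hazards confined to the first two months and continuing through the 55-day window, crude percentages agree but the rate ratio is 0.83 to 0.84. With equal hazards confined to the oxaliplatin cycles it is 0.86 to 0.88. The extra event-free time on the longer arm dilutes its rate.

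**The case against.** The strongest case for the plan has four parts.

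- The proportion of patients who have an event under treatment to progression is a legitimate quantity: it is the risk a patient faces on that regimen. This stands. A reader might infer that the crude comparison fails to answer the safety objective, but the documents do not support that. The crude percentages answer one question and leave the hazard question open.
- Safety is more than AE percentages. Laboratory values, vital signs and ECG are summarised by visit (SAP 7.2.1, 7.3, 7.5), and exposure is shown by arm. This stands, but AEs themselves have no such time-matched display.
- The distortion needs a PFS difference that is only a sample-size assumption, and treatment also stops for other reasons (Protocol 3.4), so time on treatment is not PFS. This stands. It makes the effect conditional and smaller.
- No AE hypothesis test or AE-based decision rule is specified, and SAP 2.3 allows supplemental safety analyses. The harm is therefore to descriptive interpretation. However, SAP 2.3 prespecifies nothing on this point, and an adjustment chosen after unblinding would carry less weight.

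A reader might also take neuropathy as the natural example of an accumulating event. It is a poor one if it is driven by oxaliplatin, which stops after six cycles in both arms.

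**Conclusion.** The gap is real and modest. AE comparison rests on crude percentages in a window that lengthens with PFS, and neither document plans a time-aware AE measure. If the PFS hazard ratio is 0.70, an event with an equal constant hazard would show about 2 to 7 more points on andecaliximab at 20 to 60% incidence. The low end includes an assumed 5% per month of stopping for other reasons.

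A reader might infer an excess of 6 to 9 points. That requires unlimited follow-up and stopping only at progression, which the planned accrual and follow-up rule out, so it is a ceiling. Nor will the bias necessarily appear: it vanishes as the PFS hazard ratio approaches 1 and reverses if treatment is shorter on andecaliximab. It is about 1 point or less for events in the first two months and at most about 3 points for events confined to the oxaliplatin cycles.

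The result rests on exponential time on treatment, a constant AE hazard, and illustrative incidences that the documents do not give. It is a cheap improvement to the analysis plan and does not undermine the trial's conclusions.

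**What to change.** In SAP 7.1.6.1, keep the crude tables and prespecify a supportive comparison by arm for:

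- any TEAE
- Grade 3 or higher TEAEs
- SAEs
- TEAEs leading to discontinuation of andecaliximab/placebo
- preferred terms above a stated frequency

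Use one or both of:

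1. Cumulative incidence of first event (time to first event), read at fixed times from first dose. State how death and the end of the treatment-emergent window are handled. If leaving the window is treated as a competing event, the curve ends at the crude percentage again.
2. First-event rates per person-time at risk with 95% CI, shown separately for the first six cycles and the maintenance phase.

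State that these are read beside the crude percentages when exposure differs. Do not make a single overall rate per subject-year the basis for comparison: for early-onset or oxaliplatin-phase events it would make the longer-treated arm look about 12 to 17% safer with no true difference.

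The cost is a paragraph of SAP text and a few tables from AE onset and dosing dates already collected. The period-specific rates still assume a roughly constant hazard within each period. Censoring at the end of the window assumes that patients who leave treatment have the same AE risk as those who stay.
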